## Emotional Distress

Symptoms of emotional distress will be assessed using the Patient Health Questionnaire – 9 (PHQ-9) for depression and the Generalized Anxiety Disorder – 7 (GAD-7). The PHQ-9 is designed for the screening and monitoring of depressive symptoms as well as for the presence and duration of suicide ideation. The PHQ-9 provides cut-off scores for mild, moderate, moderately severe, and severe depression. PHQ-9 scores >10 have sensitivity of 88% and specificity of 88% for major depression. The GAD-7 is designed for the screening and monitoring of anxiety symptoms. Cut-off scores are provided for mild, moderate, and severe anxiety. Using the threshold score of 10, the GAD-7 has a sensitivity of 89% and a specificity of 82% for generalized anxiety disorder. These questionnaires have undergone reliability and validity testing across individuals with range of health conditions and demographic characteristics. The PHQ-9 and GAD-7 will be administered at baseline, post-intervention, and 6-month follow-up via the RICE Platform.

## Cardiovascular Health Indices

1) Using the Dried Blood Spot (DBS) method, blood will be collected to measure:

- a. **serum biomarkers of inflammation:** interleukin [IL] IL 6, high sensitivity C reactive protein [hsCRP]
- b. **oxidative stress:** myeloperoxidase
- c. **lipid profile:** triglycerides, total Cholesterol, HDL Cholesterol

We will mail the participants a Dried Blood Spot (DBS) Kit, including written directions and a link to a video that explains the procedure in detail [<https://bcove.video/2LixHlr>]. Participants will collect about six drops of blood by pricking their finger. The 6 blood drops usually required to fill a specimen card are equal to a total blood volume of about ¼ teaspoon and the collection of a dried blood spot sample usually takes about 10 minutes. The samples will be shipped to St. Jude Children's Hospital, where they will be stored until the end of the study. At the end of the study, the Dried Blood Spot (DBS) cards will be shipped to the University of Washington for analysis. All samples will be assayed in duplicate and the average of the two measures will be used for data analyses. All samples from individual participants will be run on the same assay plate to reduce intra-assay variation. Serum biomarkers will be measured at baseline, post-intervention, and 6-month follow-up.

St. Jude Children's Research Hospital

IRB NUMBER: 19-0121

IRB APPROVAL DATE: 05/04/2021

2) Resting Heart Rate (RHR) and Heart Rate Variability (HRV) will be measured by having participants wear the WHOOP wrist monitor. We will use a time domain measure of heart rate variability (HRV), a non-invasive, albeit indirect way to investigate autonomic nervous system function. It is attractive in this large cohort study, with participants distributed around North America, because today's sensor technology allows remote collection of data in participants usual environments while doing their usual activities. We will use the WHOOP® strap wearable biosensor to obtain standard deviation of NN (normal to normal RR) intervals (SDNN) measured over a 24-hour period and recorded in milliseconds (ms). SDNN captures total HRV; low values over a 24-hour period indicate lack of circadian rhythm. We selected this measure as our primary outcome because of its documented associations with morbidity and mortality in several large studies. Data from the Framingham Heart Study (N=2501) indicate that a one standard deviation decrement in the SDNN (log transformed), captured remotely over 2 hours, is associated with a nearly 50% increased risk (HR 1.47, 95% CI 1.16-1.86) of new onset cardiac conditions, even after accounting for other known risk factors for autonomic dysfunction. In addition, among persons with congestive heart failure (UK-heart, N=433), in adjusted models, a 41.2ms decrement in SDNN, measured over 24-hours, was associated with a 1.62 (95% CI 1.16-2.44) increased risk for all-cause mortality, and the strongest predictor of death related to progressive heart failure. The WHOOP device includes a photoplethysmography-based heart rate/heart rate variability sensor, an accelerometer, and sensors to detect ambient temperature and galvanic skin response. For this study participants with 24-hour SDNN <50ms will be classified with unhealthy HRV, those with values 50-100ms with compromised HRV, and those with values >100ms with normal HRV. The participants will wear the WHOOP wrist monitor for a period of 7 to 11 consecutive days at three specified intervals [baseline, post-intervention, 6 months]. The mailing of WHOOP wrist monitors will be coordinated by study personnel at St. Jude in collaboration with the CCSS coordinating center. Participants will receive a WHOOP wrist monitor along with a pre-paid return package. The WHOOP wrist monitor will be mailed to the participant at baseline and maintained by the participant for the duration of the study. Heart rate data will be uploaded by participants using their smart phone or tablet to a secure cloud-based platform hosted by WHOOP and securely accessible by the study team at St. Jude

3) Physical Activity will be measured by having participants wear the WHOOP wrist monitor. This device includes tri-axial accelerometer that detects wrist movement, which is used to collect objective information on intensity and duration of common locomotion activities such as walking and jogging. Physical activity of each participant will be measured with the WHOOP wrist monitor, which will be worn by the participant for 7 to 11 consecutive days at three specified intervals [baseline, post-intervention, 6 months] corresponding to the same period when sleep patterns are measured.

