**Data Management: Collection of eHealth Data Using the RICE Platform:** Interaction with participants and collection of data will be accomplished using the Research Infrastructure Containing E-interventions (RICE) Platform developed at the Center for Behavioral Health and Technology at the University of Virginia by [name] (Co-Investigator). Through a subcontract with [name] and the University of Virginia, a study-specific module within the RICE Platform will be used for post-enrollment study activities. The platform will be used to: (1) provide access to instructional and demonstration videos; (2) collect data, including questionnaires; (3) implement the SHUTi program (intervention group) and educational program (control group); and (4) secure transmission of data to the study team. The platform allows for input constraints in the tools as well as real-time validation of data formats and ranges, providing real-time feedback to the user if “out-of-range” values are recorded. Participants will need to be able to access the internet on a device of their choosing.

We anticipate enrollment of 352 participants within a 4-year period.

**Human Subjects:** The risk of harm anticipated in the proposed research is not greater than that encountered during daily activities or during the performance of routine physical

**Protocol MNEMONIC and Title: SLEEPWELL: eHEALTH INSOMNIA  
INTERVENTION FOR ADULT SURVIVORS OF CHILDHOOD CANCER: A  
RANDOMIZEDCLINICAL TRIAL**

examinations. Monitoring will be performed by the PI, co-investigators, and the IRB through annual continuing reviews. All study activities will be done completely remotely, and the main requirement is to have internet access, access to a computer or laptop, and access to a smart phone or tablet. During the intervention, participants will be instructed on how to minimize the risk associated with sleep restriction and to contact study staff if they have any significant concerns. As needed, study staff will instruct participants to contact their primary care provider. Participants will not be required to complete any of the assessments they wish to omit, nor will they be required to answer any questionnaire items they do not wish to answer.

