### 3.3. Research Participant Recruitment and Screening

Recruitment will be conducted by the CCSS Coordinating Center at St. Jude. As illustrated in Figure 3 to the right, survivors participating in CCSS who have been previously identified as having neurocognitive impairment in at least one of three domains in the NCQ will be approached for recruitment. An approach packet consisting of an introduction letter, a single page study brochure, and informed consent documents will be mailed to these potentially eligible participants. Interested participants will be instructed to visit the study webpage, where participants can sign-up and provide informed consent on-line. Those who have not responded after two weeks will receive an email alerting them to the study and providing a link to the study webpage. Starting three weeks after the initial mailing, a trained study interviewer housed within the CCSS Call Center will begin calling non-responders to provide information, answer questions, and encourage participation. Eligible participants will have the opportunity to consent to the study verbally while speaking with a trained study interviewer from the CCSS Call Center. Alternatively, survivors who wish to participate will complete an online consent form and then a series of short questionnaires to determine study eligibility. This data collection will take place in DatStat Connect, which is the online consenting and data collection tool utilized for the CCSS. To date, there are 11,579 non-CNS tumor survivors who were previously administered the CCSS-NCQ. Based on those surveys, 4,465 were impaired and, conservatively we estimate that 30% of these will have comorbid symptoms of insomnia (n=1,339). We anticipate enrolling 52 participants in year 1 and 100 participants per year in years 2-4, each year divided equally by sex.

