direct relationships between change in ISI (baseline to post-intervention) with emotional distress and cardiac health indices at postintervention time points and with HRQoL measures. To establish whether a mediation relationship exists, we will follow standard methodology by 1) establishing that there is an association between the causal variable (e.g. CBTi intervention) and the outcome (e.g. neurocognitive impairment), 2) establishing the association between the causal variable and the mediator and 3) showing that the mediator is associated with the outcome variable in a model with the causal variable included and 4) in the same model as used to evaluate step 3, determine that the relationship between the causal variable and the outcome variable is attenuated by inclusion of the mediator in the model. We do not expect to observe complete mediation in any of our investigations. Specifically, the above methodology will be used to test hypothesis 1.2.2.b with the causal variable defined as CBTi intervention, mediator as change in insomnia (ISI) and outcomes as neurocognitive indices. Hypothesis 1.2.2.c will consider change in insomnia as the causal variable, neurocognitive function indices, emotional distress symptoms and cardiovascular risk indices as mediators for the outcome HRQoL at 6 months. In addition to the stepwise model-based approach outlined above, we will also evaluate relationships using Structural Equation Modelling (SEM) approaches to evaluating mediation, which would allow simultaneous evaluation of the multiple pathways and classes of variables together in a single model, with improved power, allowing estimates of direct and indirect effects calculated from each. All effects size estimates (mean differences and/or odds ratios) will be presented along with associated confidence intervals and two-sided p-values, both unadjusted and adjusted for multiple comparisons. Primary therapies for childhood cancer have been associated with insomnia and study outcomes (neurocognitive morbidities, emotional distress, cardiovascular risk). Because our study inclusion criteria require that survivors have observed neurocognitive deficits we do not expect differential responses to SHUTi by previous childhood cancer treatment exposures. However, chemotherapy exposures and radiation doses are abstracted from medical records and cumulative doses of methotrexate (high dose and intrathecal), cytarabine, and cranial radiation will be included as covariates in relevant analyses. In addition, we will conduct sensitivity analyses to examine their contributions to treatment response.

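### Blood-spot cards will differ in storage age by up to about 4 years when assayed, and the association and mediation models that use their levels do not adjust for it

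*Combined protocol and SAP*

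**What the plan says.** Section 4.3 (Cardiovascular Health Indices) collects finger-prick blood spots for IL-6, hsCRP, myeloperoxidase and lipids at three visits: "Serum biomarkers will be measured at baseline, post-intervention, and 6-month follow-up". The cards go to the trial centre, "where they will be stored until the end of the study". Then: "At the end of the study, the Dried Blood Spot (DBS) cards will be shipped to the University of Washington for analysis". On laboratory handling it adds "All samples will be assayed in duplicate and the average of the two measures will be used for data analyses" and "All samples from individual participants will be run on the same assay plate to reduce intra-assay variation". No storage temperature or stability limit is given.

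On timing, the Data Management overview in the front matter states "We anticipate enrollment of 352 participants within a 4-year period", and section 3.3 gives the rate: "We anticipate enrolling 52 participants in year 1 and 100 participants per year in years 2-4". Section 4.1 places the second evaluation about 10 weeks after baseline and the last about 6 months after that.

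In section 9.1 the arm comparison is a linear regression on change scores adjusted for the stratification factors. Methotrexate, cytarabine and cranial radiation doses are added in relevant analyses. The biomarkers enter the association analyses, which relate change in ISI to "emotional distress and cardiac health indices at postintervention time points", and the mediation analysis of HRQoL at 6 months. Section 9.1 labels that mediation analysis 1.2.2.c; section 1.2 states it as 1.2.3.b. Neither storage time nor plate is named as a covariate or sensitivity analysis.

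**The concern.** When cards collected over several years are assayed together, early participants' cards have been stored much longer than late participants' cards. If an analyte is lost in storage, the measured level is a mixture of biology and enrolment date.

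The same-plate rule deals with a different problem. It removes a shared plate effect from one person's change over time. It does not remove the age difference between that person's cards, and it gives no protection when levels are compared between people on different plates with cards of different ages.

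The section 9.1 association and mediation analyses make that comparison. Their causal variable is change in ISI, which is not randomised, so randomisation does not protect them. Two things are at stake. Storage loss adds noise that weakens associations and indirect effects. If ISI change or HRQoL also varies with enrolment date, storage age becomes a confounder.

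**Working it through.** **1. The plan's own accrual figure.** 52 + 3 × 100 = 352 in 4 years. This matches the stated total.

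**2. Gap within a person.** 10 weeks (baseline to post-intervention) + about 26 weeks (6 months) = 36 weeks = 0.69 year.

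**3. Storage age at assay.** Take enrolment as even within each year and assay immediately after the last 6-month visit, which is 4 + 0.69 = 4.69 years after first enrolment.

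- Baseline cards: 0.69 to 4.69 years
- Post-intervention cards: 0.50 to 4.50 years
- 6-month cards: about 0 to 4.0 years

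**4. Mean and SD between participants.** The mean enrolment time is (52 × 0.5 + 100 × 1.5 + 100 × 2.5 + 100 × 3.5)/352 = 776/352 = 2.20 years, so mean baseline storage is 4.69 − 2.20 = 2.49 years. The variance is (52 × 0.25 + 100 × 2.25 + 100 × 6.25 + 100 × 12.25)/352 − 2.2045² + 1/12 = 5.932 − 4.860 + 0.083 = 1.155, so the SD is 1.07 years. It is the same at every visit, because the visits are shifted by a constant.

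**5. Effect on levels.** The documents give no loss rate, so assume a constant proportional loss L per year. With d = −ln(1 − L), the observed log level is the true log level minus d × storage age. If storage age is unrelated to biology, a correlation with another variable is multiplied by 1/√(1 + (d × 1.07/s)²), where s is the assumed biological SD on the log scale. Two cards 4 years apart differ by the ratio (1 − L)⁴.

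| Assumed loss per year | d | d × SD of age | Ratio, cards 4 years apart | Factor, s = 0.3 | Factor, s = 0.5 | Factor, s = 1.0 |
|---|---|---|---|---|---|---|
| 1% | 0.010 | 0.011 | 0.96 | 1.00 | 1.00 | 1.00 |
| 5% | 0.051 | 0.055 | 0.81 | 0.98 | 0.99 | 1.00 |
| 10% | 0.105 | 0.113 | 0.66 | 0.94 | 0.98 | 0.99 |
| 20% | 0.223 | 0.240 | 0.41 | 0.78 | 0.90 | 0.97 |

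Worked entry (20%, s = 0.5): 0.240/0.5 = 0.48; 1/√(1 + 0.48²) = 1/√1.23 = 0.90.

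**6. Effect on arm contrasts of change.** In log change from baseline to 6 months, storage contributes d × 0.69. This is nearly the same for every participant, so it cancels between arms and adds essentially no variance. For levels, 2,000 simulated permuted-block allocations (assumed block sizes 4 and 6, eight equal strata) gave a difference between arms in mean storage age of 0.00 year, SD 0.03. In 95% of them it was below 0.064 year. Even at 20% loss, that is 0.223 × 0.064 = 0.014 on the log scale, about 1.4%.

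**7. Cost of fixed plate terms.** Three cards in duplicate need 6 wells per participant. Assuming 80 to 96 usable wells per plate, 280 × 6/96 = 17.5 and 352 × 6/80 = 26.4, so about 18 to 27 plates and 17 to 26 degrees of freedom. The analyses are sex-specific, with about 140 to 160 people each.

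**The case against.** The strongest reply is that the harm is assumed. No loss rate appears in the documents. At 1% per year the attenuation is nil to two decimals, and for a widely varying analyte it stays small even at 20%. That stands, and it limits the size of the point.

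A reader might also infer more than the documents support:

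- *Biomarkers will falsely appear to rise after treatment.* Under the same assumed rates the baseline-to-6-month drift would be 0.7%, 3.6%, 7.5% or 16.6%. But section 9.1 compares changes between arms, and no uncontrolled within-arm biomarker change is planned.
- *The arm comparison is biased or loses precision.* Step 6 shows that it is not materially biased, and that contrasts of log change lose essentially nothing.
- *The whole cardiovascular part of 1.2.2.c and 1.2.3.b is weakened.* Resting heart rate, heart rate variability and physical activity come from the wrist monitor and have no storage time.
- *Plate belongs as a fixed covariate in every model.* Step 7 shows the cost. If plates are filled in enrolment order, plate and storage time would also be nearly collinear.

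Three limits come from the text itself. The 4.69-year maximum rests on planned accrual and immediate assay; section 9.0 gives completion dates but no start date, so the actual range cannot be fixed. The mediation paragraph in 9.1 begins mid-sentence in the available text, so some analysis wording may be missing. The kit's written directions are not shown, so it cannot be said that collection dates go unrecorded.

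None of this supplies the missing adjustment. The association and mediation analyses still compare levels between people, and neither randomisation nor the same-plate rule covers them.

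**Conclusion.** The point holds as a cheap improvement to a limited set of secondary analyses. Under the planned accrual, cards from different participants differ in storage age by up to about 4 years (SD about 1.07 years), and the visible analysis text does not adjust for it. Only the section 9.1 association and mediation analyses that use blood-spot levels across people are exposed. There, correlations shrink by a factor of between 1.00 and 0.90 for assumed losses of 1% to 20% per year at a log-SD of 0.5. The shrinkage is larger for analytes that vary less (0.78 at 20% and a log-SD of 0.3). Confounding arises only if ISI change or HRQoL also varies with enrolment date, which the documents neither show nor exclude.

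The loss rates and log-SDs are assumptions. The 36-week gap follows from the visit schedule, and the 4-year spread from the planned accrual. The ISI primary endpoint, the stated power, arm contrasts of change and the wrist-monitor indices are not called into question.

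**What to change.** In section 9.1, prespecify storage duration (collection date to assay date) as a single covariate in the models that use blood-spot biomarker levels. Handle plate as a random effect or in a sensitivity analysis, not as fixed terms in every model. Confirm that both dates are carried into the analysis data set.

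In section 4.3, keep each participant's cards on one plate, but allocate participants to plates balanced by arm and not in enrolment order, so that plate and storage time can be separated. This has to be settled before the cards are assayed.

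The cost is one degree of freedom per model and a plate-layout instruction to the laboratory, with no extra samples or assays. If storage loss turns out to be small, the gain is small too.

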## Quality of Life

Health-related quality of life (HRQoL) will be assessed at baseline, post-intervention, and 6-month follow-up. HRQoL will be measured with the PROMIS Global Health questionnaire. This is a widely used 10-item generic health profile that provides physical and mental health summary scores. The Global Health measure will be completed via the RICE Platform.

## Exploratory Outcomes

In addition to quality of life we will evaluate, in an exploratory manner, the impact of improved insomnia symptoms on work and social adjustment 6-months post intervention. The work productivity and activity impairment questionnaire (WPAI) is a 6-item measure that assesses work-related impairment reflected by amount of absenteeism, presenteeism, and daily activity measures. This measure has good discriminatory and construct validity, as well as the ability to detect significant changes in symptoms. The work and social adjustment scale (WSAS) measures social and work-related impairment resulting from mental health problems. The internal consistency is high, with Cronbach's  $\alpha$  ranging from .70 to .94 and test-retest reliability is also good ( $r=0.73$ ). The WPAI and WSAS will be completed by participants via the RICE Platform.

### 4.4. Intervention

Participants will receive a direct link to access the SHUTi program or online patient education (per randomization) from the study team. This will include login and password information. Through the RICE platform, St. Jude study staff will track and monitor participants who are randomized to SHUTi or patient online education.

#### SHUTi

SHUTi is a fully automated, interactive and tailored web-based program that incorporates the primary tenets of face-to-face CBT-I, including sleep restriction, stimulus control, cognitive restructuring, sleep hygiene, and relapse prevention. Intervention content is presented in six "Cores," metered out over time. Each Core

was developed to parallel traditional weekly sessions conducted when delivering CBT-I in a face-to-face format, following a similar general structure: 1) examination of Core objectives, 2) review and feedback on homework and sleep diary data from the previous week, 3) teaching of new intervention material, 4) summary of the main points of the Core, and 5) assignment of homework. The participant will have nine weeks to complete the six cores and at week 10 will be asked to complete post-intervention questionnaires/sleep diaries as well as to complete the post intervention remote evaluation. Data will be available on total number of participant logins, sleep diaries completed, and core modules completed. All participants will be able to access human support through UVA for technical difficulties with SHUTi. Intervention content is enhanced through

St. Jude Children's Research Hospital

IRB NUMBER: 19-0121

IRB APPROVAL DATE: 05/04/2021

a variety of interactive features, including personalized goal-setting, graphical feedback based on reported symptoms, animations and illustrations to enrich comprehension, quizzes to test and enhance user knowledge, vignettes to promote identification with material, and video-based expert explanations. Weekly automated emails are also sent to increase engagement and encourage program adherence. However, no human support will be provided to increase treatment adherence. Removing human support from provision of care can vastly increase the ability to widely disseminate treatment, however, it may be associated with reduced adherence. Despite this, a recent study of SHUTi with breast cancer survivors indicated that intervention group participants completed 4.1 (SD = 2.5) cores, with 82.1%, 75.1%, 67.2%, 64.2%, 62.7%, and 59.7% completing cores 1, 2, 3, 4, 5, and 6, respectively. The number of cores completed was associated with improvements in insomnia symptoms. Therefore, we will complete a sensitivity analysis to examine the impact of treatment adherence on insomnia symptoms.

